# 3.2 Study Flow

Patients will undergo assessments during a (maximum) 28-day screening period, pre-dose and periodically during treatment, as outlined in Section 6. For both regimens of KY1044 administration as single agent and in combination with atezolizumab, treatment will continue until a patient experiences unacceptable toxicity, progressive disease as per iRECIST and/or withdrawal of consent.

Safety follow-up will be performed 90 days after the end of treatment.

Patients who do **not** have progressive disease (as per RECIST 1.1/iRECIST) at the time of discontinuing treatment will receive tumor assessments for evaluation of PFS until disease progression, or starting alternative treatment or the overall end of study (EOS) if earlier (see Section 8.2.1).

All patients who do not withdraw consent for the study will be followed up for survival unless they are lost to follow-up, or overall EOS has been declared (see Section 3.6).

Figure 3-2: Study Flow per Patient

\* Note: Additional provisions may be made for patients who are ongoing on treatment and are still receiving clinical benefit at 48 months for continuation of treatment.

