# 5.3 Treatment Duration

All patients treated with either KY1044 as single agent or in combination with atezolizumab will begin study treatment on Cycle 1 Day 1. Each cycle will consist of 21 days ( $\pm$ 3 days). The next scheduled dose (as single agent or in combination) may be delayed by up to 7 days to recover from previous Aes. If the next dose (as single agent or in combination) cannot be administered within the above mentioned 7-day delay, then the dose should be skipped. Dosing will resume at the scheduled dose or the next lower dose. Dose modifications should follow Section 5.6.

If more than one consecutive dose of KY1044 as single agent or in combination with atezolizumab has to be skipped due to study treatment-related toxicities, then the default position is that IMPs should be permanently discontinued. However, if a patient who misses more than one consecutive dose due to a study treatment-related toxicity experiences clinical benefit, and in the opinion of the Investigator it is in the patient's best interest to remain on study, then the patient may continue treatment after discussion with the Medical Monitor.

A patient may continue treatment with KY1044 as single agent or in combination with atezolizumab within this clinical study, as long as they are continuing to derive benefit from treatment, until the patient experiences unacceptable toxicity or confirmed disease progression per iRECIST. Patients will not be withdrawn from the study due to progressive disease per RECIST 1.1, unless clinically indicated.

Criteria for treatment cessation or patient withdrawal from the study are outlined in Section 8, and management of toxicities is outlined in Section 5.6.

Patients with SD, PR, unconfirmed CR, and unconfirmed progressive disease will continue treatment in additional cycles.

Patients who meet the following criteria will NOT continue treatment in additional cycles:

- Patients who experience unacceptable toxicity.
- Patients with confirmed progressive disease. These patients will enter the Safety follow-up period unless the Investigator considers it to be in the patient's best interest to remain on the study, and after discussion with the Medical Monitor.

• Patients with an unconfirmed progressive disease who show signs of clinical deterioration or toxicity. These patients will enter the Safety follow-up period, and will continue to be followed-up until confirmed progressive disease or initiation of a new treatment.

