### 6.2 Assessment of Efficacy

#### 6.2.1 Tumor Assessments

Tumor response will be determined locally according to two sets of criteria:

- RECIST 1.1: Appendix 1 (51, 52)
- iRECIST: Appendix 2 (53)

The Investigator's assessment according to both RECIST 1.1 and iRECIST will be used for the analysis of response and for treatment decisions (study discontinuation due to progressive disease as per iRECIST). During the course of the study, the Sponsor may decide to have a central review of the radiological assessments performed. In such case, the Investigator's staff will be instructed on how to send data from these radiological assessments to a CRO for central review when needed.

RECIST 1.1 guidelines for measurable, non-measurable, target lesions (TLs) and non-target lesions (NTLs) and the objective tumor response criteria are presented in Appendix 1 of this protocol.

Screening tumor assessments will include CT of the thorax and abdomen (including liver and adrenal glands) and pelvis and should encompass all areas of known predilection for metastases in the disease under evaluation and will additionally investigate areas that may be involved based on signs and symptoms of individual patients. Brain magnetic resonance imaging (MRI) is mandatory for patients with known or suspected brain metastases.

If a patient is intolerant to iodine-based contrast agents, CTs may be performed without contrast. MRI may be used to evaluate sites of disease where a CT without IV contrast is not adequate or to evaluate sites of disease that are not adequately imaged by CT. Ultrasound should not be used to measure sites of disease.

Screening assessments should be performed no more than 28 days before the start of study treatment, and ideally should be performed as close as possible to the start of study treatment. Scans obtained as part of standard clinical practice, prior to informed consent, but within the 28-days prior to treatment are acceptable.

The methods of assessment used at screening should be used at each subsequent follow-up assessment every 8 weeks ( $\pm$ 7 days) after the start of treatment for 16 weeks, after that every 12 weeks ( $\pm$ 7 days) for 48 months of treatment of duration or until objective disease progression as defined by RECIST 1.1/iRECIST (see Table 6-3). Scans confirming progression should preferably not be conducted within 1 week of a progression biopsy to allow for reduction in inflammation.

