# 8.1 Follow-up of Patients Off Treatment

If a patient needs to withdraw from study treatment for AEs or other safety reasons (reasons 3 and 4 above), but does not have disease progression, they will continue with tumor progression assessments in accordance with the study schedule until they progress as per iRECIST or until they start another anti-cancer therapy or when the overall end of the study is reached. Patients who withdraw consent to treatment but who accept continued monitoring (see Section 6.2.1) will also continue in the same way. Continuation of patients who stop treatment for reasons of non-compliance should be discussed between the Investigator and the Medical Monitor.

All patients (all reasons 1 to 6 listed above) will be followed up at 3 monthly intervals (telephone followup is acceptable) to obtain survival information after the start of treatment. These data will be recorded in eCRF.

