#### 8.2.2 Follow-up Period

All patients must have 90 days safety follow-up evaluations after the last dose of study treatment, including tumor or survival assessments. Evaluations should be performed according to the schedule of assessments, and data collected added to appropriate eCRF pages.

Patients who discontinue study treatment and do not have progressive disease per RECIST 1.1/iRECIST, but continue with study assessments will return for tumor assessments (Section 6.2.1) according to the study schedule. Any relevant adverse event data reported during study visits will be recorded. No other study procedures will be performed. Tumor assessments will stop when disease progression is confirmed (RECIST 1.1), the patient commences further treatment for their malignancy, or when the overall end of the study is reached. The date at which tumor monitoring is discontinued must be recorded. After discontinuation of tumor assessments patients will continue to be followed up for survival status at 3-monthly intervals.

All patients who do not withdraw consent for the study will be followed up for survival unless they are lost to follow-up or the overall end of the study has been declared.

Property of the Sanofi Group - strictly confidential

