8.6.4 Progression Free Survival

PFS is defined as the time from the first dose of study drug to the date of progression of disease or death (event) due to any cause, whichever occurs first. PFS (in months) will be calculated as:

(first event/censored date – first dose date of study drug +1)/30.4375.

The clinical progression without further radiological assessment as corroboration will not be considered as progressive disease.

Using iRECIST, PFS is defined as the time from the first dose of study drug to the date of death or the of first documented tumor progression (iUPD) provided that iCPD is confirmed at the next assessment, whichever is earlier.

The patients who have not progressed or died at the time of analysis will be censored. Following censoring rules will be applied for PFS:

Patients with no disease assessment (or only have assessment(s) with response = NE) after first study treatment or have baseline or post-baseline assessments where the RECIST criteria cannot be applied (e.g. not all baseline lesions assessed) will have their PFS time censored on the date of first dose with duration of 1 day unless they die within 2 tumor assessments of baseline, then they will be treated as an event with date of death as the event date.

Event time will be censored on the date of the last evaluable assessment documenting absence of progression of disease for:

- Patients on-study and progression-free at the time of analysis;
- Patients who have progression of disease or death on study after ≥2 consecutive missed tumor assessments;
- Patients given alternative cancer treatment prior to progression of disease or death on-study.

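### Protocol 8.1 and 8.2.2 name different criteria for ending off-treatment scans, so whether a progression counts in iRECIST PFS may depend on which section a site follows

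*Protocol*

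**What the plan says.** Protocol 8.2.2 defines its group this way: "Patients who discontinue study treatment and do not have progressive disease per RECIST 1.1/iRECIST, but continue with study assessments will return for tumor assessments". For that group, "Tumor assessments will stop when disease progression is confirmed (RECIST 1.1"), with new anti-cancer treatment and the overall end of study as the other stopping points.

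Protocol 8.1 deals with patients who leave treatment for adverse events or other safety reasons without progression, and with those who withdraw from treatment but accept monitoring. It says "they will continue with tumor progression assessments in accordance with the study schedule until they progress as per iRECIST", again subject to new therapy or end of study.

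Protocol 5.3 has a separate rule for patients who stop with unconfirmed progression together with clinical deterioration or toxicity. They "will continue to be followed-up until confirmed progressive disease or initiation of a new treatment".

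Protocol 3.2 provides that patients who at discontinuation do not have progression by RECIST 1.1/iRECIST "will receive tumor assessments for evaluation of PFS until disease progression, or starting alternative treatment". Protocol 6.2.1, to which 8.2.2 refers for the assessments, runs the schedule "until objective disease progression as defined by RECIST 1.1/iRECIST (see Table 6-3").

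SAP 8.6.4 dates the iRECIST PFS event at the first iUPD "provided that iCPD is confirmed at the next assessment", or at death if earlier.

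**The concern.** The two criteria behave differently in this protocol. The comparison table in Appendix 2 states that RECIST 1.1 progression needs no confirmation unless it is equivocal, whereas iRECIST progression does. A stop rule labelled RECIST 1.1 and a stop rule labelled iRECIST can therefore end imaging at different scans in the same patient.

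The iRECIST PFS analysis depends on the scan after the first progression. If that scan is not done, pseudoprogression cannot be told from true progression and the SAP definition has nothing to confirm the event with. The patient is censored rather than counted, which tends to lengthen iRECIST PFS. The difference would come from how a site reads the protocol and not from the disease.

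**Working it through.** No sample size, power or error rate bears on this point, so the check sets the rules side by side and follows a patient through them.

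**The stop rules**

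| Section | Patients | Imaging or follow-up ends at |
|---|---|---|
| 3.2 | Off treatment, no progression per RECIST 1.1/iRECIST | Progression; confirmation not mentioned |
| 5.3 | Stopped with unconfirmed progression plus deterioration or toxicity | Confirmed progression; criterion not named in that sentence |
| 6.2.1 | General schedule | Progression per RECIST 1.1/iRECIST, not separated |
| Table 6-3 | Body imaging, labelled for the treatment period only | Progression per iRECIST, or withdrawal |
| 8.1 | Stopped for adverse events or safety, no progression | Progression per iRECIST |
| 8.2.2 | Off treatment, no progression per RECIST 1.1/iRECIST | Progression confirmed, labelled RECIST 1.1 |

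The 8.1 patients fall within the 8.2.2 group, so both rules apply to them.

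**One patient, two readings of 8.2.2.** Suppose a patient stops for an adverse event with stable disease, and a later scan shows a first RECIST 1.1 progression. Under iRECIST this is iUPD.

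- *Reading A: confirmed means established by RECIST 1.1.* Scans stop here. There is no next assessment, so iCPD cannot be assigned. Under SAP 8.6.4 the iUPD is not an iRECIST PFS event unless the patient dies. Otherwise the patient is censored at the last evaluable scan showing no progression. Even a later death may be censored, because the SAP censors deaths that follow two or more consecutive missed assessments and does not say whether scans no longer scheduled count as missed.
- *Reading B: confirmed means seen again on a repeat scan.* One further scan is done. If it shows sufficient further growth, iCPD is assigned and the event is dated to the first scan. If the disease shrinks enough to meet iSD, iPR or iCR, the status resets. If it is unchanged, Appendix 2 keeps it at iUPD. RECIST 1.1 progression has then been seen twice, so 8.2.2 could stop scans while 8.1 would continue them.

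The unchanged case needs one qualification. For target lesions Appendix 2 requires a further increase of at least 5 mm, but Protocol 6.2.1.2 accepts an increase of at least 20% over the nadir at two consecutive visits. For target lesions the residual gap under Reading B therefore exists only if Appendix 2 governs. For non-target and new lesions, both texts require worsening or additional lesions.

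**Patients who stop with unconfirmed progression.** Confirmation is defined by a scan, so the 5.3 rule implies imaging. These patients already meet RECIST 1.1 progression. Sections 3.2 and 8.2.2 give off-treatment scans only to patients without progression per RECIST 1.1/iRECIST. If progression by either criterion excludes a patient, this group has no scheduled scan. If the slash means progression by both, they are included. The text does not settle it.

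**What the SAP does without a later scan.** Appendix 2 keeps the iUPD date in listed situations, including where no further assessment is done or where iCPD never occurs. SAP 8.6.4 does not carry that rule over.

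**The case against.** A reader might infer that 8.2.2 makes the confirming scan impossible. The documents do not support that. Section 8.2.2 does say confirmed. It sends patients to 6.2.1, whose RECIST 1.1 subsection contemplates repeat scans that confirm progression and whose iRECIST subsection says a confirming scan is required in this study, at least 4 weeks later. Reading B is therefore reasonable, and 8.1 itself does not use the word confirmed. What remains is that the repeat-scan remark in 6.2.1.1 follows a paragraph about investigator doubt, the requirement sits in the iRECIST subsection while 8.2.2 cites RECIST 1.1, and the 4 to 8 week confirmatory scan in the footnotes to Tables 6-1 and 6-2 is written for patients who continue treatment. Neither reading is excluded.

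A reader might also infer that 5.3 flatly contradicts 8.2.2 for the same patients. It does not: 5.3 concerns patients already in unconfirmed progression, and 8.2.2 concerns patients without progression. The weakness there is a possible gap in coverage.

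It is fair to add that the consequence is contained. Phase 2 ORR per RECIST 1.1 and RECIST 1.1 PFS do not use a post-progression scan, all summaries are descriptive, and new anti-cancer therapy ends imaging under every section, which removes some patients on any reading.

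**Conclusion.** The inconsistency is real and worth correcting, at the level of a secondary endpoint. Sections 8.1 and 8.2.2 name different criteria for overlapping patients, and on one of two plausible readings of 8.2.2 a true progression becomes a censored iRECIST PFS time. On the other reading a narrower gap remains for disease that is unchanged at the repeat scan, subject to the qualification on target lesions above. Patients who stop with unconfirmed progression may also lack scheduled imaging.

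The patients exposed are those who stop without progression and then show a first progression before new therapy, and those who stop with unconfirmed progression. Their number cannot be derived from the documents, and no percentage should be attached to it. The conclusion rests on SAP 8.6.4 being applied as written, with no fallback for an iUPD that has no later scan.

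**What to change.** 1. Reconcile Protocol 3.2, 5.3, 6.2.1, 8.1 and 8.2.2 on one stop criterion for endpoint imaging. In 8.2.2, replace the RECIST 1.1 label with iRECIST-confirmed progression, or new anti-cancer therapy, withdrawal or end of study, and make 8.1 and 3.2 say the same.
2. State that this covers patients who stop with unconfirmed progression, so that 5.3 has imaging behind it.
3. Say which definition of confirmed progression is meant, 6.2.1.2 or Appendix 2, and which timing applies off treatment. The footnotes to Tables 6-1 and 6-2 give 4 to 8 weeks, whereas 6.2.1.2 prefers the next scheduled visit, which after the first 16 weeks is 12 weeks away.
4. Add a rule to SAP 8.6.4 for an iUPD with no later assessment, for example the Appendix 2 rule that keeps the iUPD date. The reasons Appendix 2 lists for a missing assessment are refusal, non-compliance and death, so the SAP should say expressly whether a stop directed by the protocol is included.

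The cost is protocol and SAP wording, plus one or occasionally more further scans for some off-treatment patients, which 8.1 and 5.3 already imply. It cannot be capped at one scan, because under Appendix 2 iUPD can be assigned repeatedly before it is confirmed or reset.

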#### 8.2.3 End of Study for Individual Patients

The end of study for each patient will be either:

- At the end of the 90 day safety follow-up period after stopping treatment, for the last patient in the study
- At the overall end of the study for all patients, who are still in follow-up- for PFS and or survival as determined by the Sponsor, is defined as the date of the last visit of the last participant in the study or last scheduled procedure shown in the Schedule of Activities for the last participant in the trial globally.

The end of the study will be recorded in the eCRF.

### 8.3 Replacement Policy

### 8.3.1 Phase 1 Dose Escalation Parts:

Patients will not be replaced on study. However, if a patient is considered to be non-evaluable for the dose escalation, enrolment of a new patient to the current cohort will be considered if there is less than the required number of evaluable patients (see Section 5.4.5.1). Enrolment of new patients may be considered until at least the minimum number or at most the maximum number of evaluable patients is achieved within the cohort. Minimum and maximum numbers of evaluable patients per cohort are defined in Section 4.1.1.

### 8.3.2 Phase 2 Part:

During the Phase 2 part no replacements of patients will be needed.

# 9 STATISTICAL CONSIDERATIONS

# 9.1 Modified Toxicity Probability Interval (mTPI-2) Design

### 9.1.1 Rationale for mTPI-2 Design

The rationale for deciding the starting dose and investigational dose range are discussed in the previous Section 5.4.1. In the trial, dose escalation/de-escalation decisions will use predefined DLT criteria (Section 5.5) and be based on the mTPI-2 design (49) with precalculated decisions that are displayed in Figure 9-1 (obtained via U-Design v1.0, udesign.laiyaconsulting.com). Figure 9-1 consists of all the dose-escalation rules for the trial. The trial is conducted aiming at a target 30% DLT rate ( $p_T=30\%$ ) for the MTD with an acceptable DLT range of 25% to 35%, and a maximum sample size of 36 patients with a cohort size of 3. To begin the trial, treat three patients on the starting dose. After observing all the outcomes of each cohort (or as specified in Section 5.4.3 if cohort modification is required), dose-escalation, de-escalation or staying at the current dose will be guided by the decision table and the SRC.

### Figure 9-1: mTPI-2 Decision Table

Sample size=36, Target toxicity probability=0.3, epsilon 1=0.05, epsilon 2=0.05

\* Column indicates the number of patients treated. Row indicates the number of patients with DLTs

\*  $\mathbf{E}$ : Escalate to the next higher dose;  $\mathbf{S}$ : Stay at the same dose;  $\mathbf{D}$ : De-escalate to the previous lower dose;  $\mathbf{D}$ : De-escalate to the previous lower dose and the current dose will never be used again in the trial. Two parameters e1 and e2 are set at default values (Guo. et al. 2017) of 0.05.

The mTPI-2 design is chosen for this trial because it has demonstrated superior operating characteristics when compared with standard methods, such as the 3+3 design, and is easy to implement with precalculated dose decision rules (56).

Section 9.1.2 presents comprehensive simulation results of mTPI-2 and its operating characteristics. See Appendix 4 for the detailed technical summary of the design and simulations.

#### 9.1.2 Simulation Results

Simulations were performed via U-Design v1.0 to assess the performance of mTPI-2 based on the setting of this trial. There are seven prespecified doses and the stating dose is 0.8 mg. The sample size is 36 and patients are enrolled in cohorts of size 3. The MTD target toxicity probability is  $p_T=0.3$  and the choices of  $e_1$  and  $e_2$  are both 0.05. Six different scenarios were investigated in the simulation studies, as shown in Table 9-1 and Figure 9-1. For each scenario, 5000 simulated trials were conducted.

Index		naim	Dose (mg)						
	p T	nsim	0.24	0.8*	2.4	8	24	80	240
1	0.3	5000	0.001	0.005	0.022	0.0831	0.269	0.599	0.858
2	0.3	5000	0.668	0.832	0.924	0.968	0.987	0.995	0.998
3	0.3	5000	0.002	0.008	0.039	0.168	0.500	0.832	0.961
4	0.3	5000	0.001	0.018	0.269	0.881	0.993	0.9997	0.99998
5	0.3	5000	0.063	0.083	0.109	0.142	0.182	0.231	0.289
6	0.3	5000	0.039	0.083	0.168	0.310	0.500	0.690	0.832

 Table 9-1:
 Six Scenarios Used in Simulation Results

\*starting dose

The simulation results are presented in Figure 9-2 and Table 9-2.

Figure 9-2 illustrates the performance of mTPI-2 in terms of the probability of selecting the MTD, probability of toxicity, probability of selecting a dose higher than the MTD, and the probability of no selection.

Table 9-2 provides a summary of these results. The full details of each of the six simulations is presented in Appendix 4.

Figure 9-2:	mTPI-2 Performance	Across	the Six	Scenarios
-------------	--------------------	--------	---------	-----------

